6.1.3. Patient participants (Nested qualitive study)

A sub-sample of up to 40 patient participants (6-7 from the 6 clusters in the intervention arm) will be purposively sampled. The participants will have consented to be contacted by the Research Fellow during enrolment for the main study. The qualitative interview will be conducted within 1-2 weeks following the participant's pre-assessment consultation. The local PI, or delegate, will inform the Research Fellow when participants have attended their usual-care pre-assessment clinic consultation. The Research Fellow will telephone the participant within 1 week of the consultation to ascertain their willingness to continue participating in the study. For participants who wish to continue, a date for the qualitative interview (telephone or video) will be arranged. Verbal informed consent will be reconfirmed by the Research Fellow before the start of the interview and audio recorded.

6.1.4 Cardiology team participants (Nested qualitive study)

During site set up and training, Cardiology Department staff in the intervention arm will be informed that they will have the opportunity to participate in a qualitative interview once all recruited patient participants at their site have completed their pre-assessment consultation. The

local PI, or delegate, will identify NHS staff involved in the patient pathway for planned "angio query proceed", coronary angioplasty, and/or the delivery of CONNECT study procedures at their site. All eligible participants will be emailed a study pack (invitation letter, PIS and oral informed consent form) and invited to email, or telephone, the Research Fellow leading the qualitative study if interested in participating. Informed consent will be obtained by the Research Fellow. See section 5.2 for a description of the oral informed consent process.

6.2. Randomisation

The eight Cardiology Departments are the units of analysis and will be randomised using stratified block randomisation with an allocation ratio of 3:1 to the intervention group and block size of four. Cardiology Departments will be stratified as appropriate, by factors such as the presence, or absence, of on-site surgical provision.

Details of the Cardiology Departments in England that have expressed an interest in participating in the study through the submission of an Expression of Interest document will be recorded. A separate linkage file will be developed by the Chief Investigator or delegate (Co-Lead, Research Fellow) in which each Cardiology Departments will be anonymised through the allocation of a unique identifier. In this way the identity of participating Cardiology Departments will be blinded to the study statistician, who will generate the allocation sequence (computer generated random numbers) and implement it.

The allocation ratio was chosen to maximise the number of clusters in the intervention arm to test the feasibility, practicality, and acceptability of the intervention. A control arm was included to evaluate the feasibility and acceptability of trial procedures such as the willingness of Cardiac Departments to be randomised. This study is not a 'mini-version' of the future c-RCT designed to test the effectiveness of the intervention.

6.3 Blinding

Participating Cardiology Departments will be randomised to the intervention or control group after they have agreed to participate. The statistician conducting the randomisation will be blinded to the identity of the Cardiology sites. A cluster design was chosen for this feasibility study to minimise the contamination that could result from allocating patient participants to either an intervention or control within a cardiology department. It would not be possible to blind participants to their allocation to the intervention or control.

7. STUDY INTERVENTION AND USUAL CARE

7.1 Usual care and site requirements

Before opening the study, all Cardiology Departments will receive study-specific training on the logistical and operational aspects of the study. As part of this process, we will map the patient pathway to understand the number and duration of patient contacts. Cardiology Departments randomised to the control arm will not receive training about CONNECT or shared decision-making and will deliver standard care. However, for equity, we will offer Cardiology Departments in the control arm the option of completing training on shared decision-making at the end of the study if desired. Information about treatment options will be provided to patients in the control arm during the referral consultation and at the pre-assessment consultation as usual (See Figure 1). Participants in the intervention and control arms will complete identical questionnaires. To understand how usual care compares with the intervention and potential sources of contamination, we will ask Cardiology Department to provide us with copies of any written or

digital material provided to patient participants regarding their treatment (coronary "angio query proceed" and planned coronary angioplasty). We will also include a question on the Angioplasty Knowledge Questionnaire about the format and content of any health information they received before their treatment, as part of usual care.

7.2 PtDA CONNECT

CONNECT (COroNary angioplasty dECision Tool) is a digital Patient Decision Aid hosted on a university website. Like other PtDAs, CONNECT is an intervention designed to encourage patient involvement in health-related decision-making. CONNECT is not a medical device. It is an educational tool, that goes beyond simply providing information. It uses multimedia (images, diagrams, animations, audio) to inform patients about their treatment choices and the associated risks and benefits of each. Through interactive activities (i.e., questions about angina symptoms, what matters to them and their preferred treatment choice) CONNECT enables users to clarify and communicate their personal values in relation to each treatment option. CONNECT generates a personalised summary derived from self-report questionnaires that can be saved as a PDF file. The summary identifies self-reported angina symptom burden and the impact on daily life, personal values, treatment preferences, worries, concerns, and unanswered questions. This personalised summary can inform patient consultations and potentially act as a 'primer' for health professionals, alerting them to specific areas that the patient may wish to discuss. See appendix 1. for a detailed description of CONNECT using the template for intervention description and replication (TIDieR) checklist²⁰. CONNECT is accessible at the following link https://uoh-replication (TIDieR) checklist²⁰. CONNECT is accessible at the following link https://uoh-replication (TIDieR) checklist²⁰. connect.staging.ginger-root.co.uk/

Patient participants at the Cardiology Departments in the intervention arm will receive information about how to access CONNECT either as part of usual care correspondence from the hospital confirming their pre-assessment consultation and/or procedure date. The information about CONNECT and the weblink or QR code will be delivered on a paper or digital letter, email, or text message, depending on the usual approach adopted by the Cardiology Department. Or, if this approach does not align with the patient pathway of care, then a Clinical research nurse will send CONNECT access instructions 1-2 weeks after consent.

Participants will be invited to use CONNECT and save their personal summary before attending their usual-care pre-assessment clinic consultation. To standardise the delivery of CONNECT across Cardiology Departments, we will create training materials that will be delivered during site set up.

7.3 Compliance with Intervention

In this feasibility study, adherence to CONNECT will be conceptualised as the percentage of patient participants who report being able to successfully access CONNECT. In addition, we will ask the patient participant and pre-assessment nurse if the CONNECT summary was taken to the pre-assessment consultation.

7.4 Use of CONNECT after study completion

We will make CONNECT available to those sites who wish to continue to use it providing it remains available on the website.

8. OUTCOME MEASURES AND STUDY PROCEDURES

8.1 Feasibility and nested qualitative study outcomes

Table 2. shows an overview of the outcomes for the proposed feasibility study and nested qualitative study.

Table 2: Overview of feasibility study uncertainties and outcomes

Uncertainty	Outcomes
Feasibility of cluster recruitment and their willingness to participate	 Number of Cardiology Departments approached, the number of responses to the 'Expression of Interest', and the number willing to participate. Recruitment rate (Number of Cardiology Centres recruited in 4 months).
Feasibility of patient participant recruitment and retention	 Number of eligible patient participants, approached, consented, and recruited. Recruitment rate (Number of patients recruited per month, per site). Retention rate, defined as the proportion completing the anticipated primary outcome questionnaires (Decisional Conflict Scale questionnaire at T2). Attrition (loss of participants who were assigned to intervention or control). Rates of MACE and hospital readmission within 30-days of discharge.
Diversity and inclusivity of sample	 Characteristics of Cardiology Departments: geographical location, Index of Multiple Deprivation (IMD), size of cardiology workforce, presence or absence of on-site surgical cover, annual volume of planned angio/coronary angioplasty procedures. Patient participant demographics: age, gender, ethnicity, level of social support, health and E-literacy, cardiac diagnosis, co-morbidities. Number of non-English speaking participants requiring interpreter services (verbal and/or translation of documents). Number of participants without access to digital technology (including smartphones, tablets, laptops, and the internet).
Characteristics and appropriateness of questionnaires as outcome measures in the future c-RCT	 Response rate (Number of participants who completed and returned the questionnaires divided by number of participants in the sample). Item response rate (Number of valid responses divided by total number of responses requested).
Intra-cluster Correlation Coefficient (ICC) and sample size calculation for full scale c-RCT	 Estimate of the ICC of the Decisional Conflict Scale at T2 using a marginal or random effects model. The full c-RCT sample size will be calculated based on estimates of the effect size (alongside previous research), the standard deviation and the ICC from the anticipated primary outcome analysis.

Uncertainty	Outcomes
Practicality of implementing CONNECT in NHS settings	 CONNECT implementation: Number of participants who access CONNECT. Percentage of pre-assessment clinic visits in which the CONNECT summary was used during the consultation. Qualitative analysis of training session minutes and interview transcripts to summarise: Potential variations in usual-care patient pathway for planned coronary angioplasty. Practicalities of providing a digital PtDA in the NHS. Barriers and enablers to integrating the CONNECT summary.
Reasons for non- consent to study participation	Qualitative analysis to summarise: Reasons for Cardiology Departments nonparticipation. Reasons for patient nonparticipation.
Acceptability of CONNECT and study procedures	 Qualitative analysis of interviews to explore: Self-reported adherence to CONNECT and how it was used by patients at home and during the pre-assessment clinic. Barriers and enablers to recruitment and using CONNECT at home and during pre-assessment clinic. Understanding, appropriateness, and potential burden of questionnaire completion.

8.2 DATA COLLECTION

Feasibility data will include logged numeric and narrative data, data from self-administered questionnaires and in-depth interviews. Table 2 provides a detailed overview of data (see pages 22-24). Table 3. shows an overview of enrolment, interventions and assessments for site set-up and the study period.

Table 3. Study Activities			Study Period						
	Site set-up	Recruitment		Data collection				Follow- up	
Approximate Timepoints**	- 3 mths	- 1-2 wks	0	+1-2 wks	+1 mths	+ 2 mths	+ 2.5 mths	+ 1-6 mths	
Cluster Expression of Interest	Х								
Cluster set-up and training	Х								
Patient identification		Х							
Patient 'Study Packs' sent to patient participants.		Х							
Member of Clinical Research Team approaches patient			Х						
Informed consent			Х						
Enrolment: Patient demographics, medical history and health and digital literacy levels			Х						

Baseline questionnaires (T1)		Х				
CONNECT link given at time of receiving pre-assessment consultation date letter			Х			
Usual care pre-assessment clinic				Х		
Post pre-assessment clinic questionnaires (T2)				Х		
Interview					Х	
Medical record review						Χ

^{**}Times will vary across Cardiology Departments due to variations in the patient pathway and waiting times for planned coronary angioplasty procedure.

8.2.1 Patient identification

During patient identification a member of the direct care team (local PI, or delegate), will identify eligible patients, approach them giving introductory information about the study, and seek permission to access their medical records and share personal details (name, hospital number, address and telephone number) with Clinical Research Nurse, or delegate. The local PI, or delegate, will complete the Patient Identification Log, which will determine the following outcomes:

- Number of eligible patients.
- Number of patients approached by the local PI or delegate.
- Number of patients who were unable, or declined, to be contacted.
- Number of patients who agreed to be contacted by the research nurse.
- Number of non-English-speaking participants requiring interpreter services

8.2.2 Patient recruitment and enrolment

A Clinical Research Nurse, or delegate, will liaise with the local PI, or delegate, and send study information pack to interested patients. The Clinical Research Nurse, or delegate, will then telephone eligible patients 3-5 days later. Completion of the Screening Log and the Enrolment and Withdrawal Log will determine the following outcomes:

- Number of patients approached by the Clinical Research Nurse.
- Number of patients who were unable to be contacted.
- Number of patients who declined participation, with reasons, where given.
- Number of participants without digital access (internet or device).

Following informed consent and enrolment into the study, the research nurse will administer the 3-item BRIEF Health Literacy Screening Tool²¹ and the 8-item eHEALS: eHealth Literacy Scale²² to participants during the telephone call and record responses in the electronic questionnaire document and enter the data into the site's Case Report Form. The Clinical Research Nurse, or delegate, will also remind participants to complete and return the baseline (T1) questionnaires, which will have already been sent to participants with the study information pack. They will also document the outcomes below in a Case Report Form:

- Patient participant demographics such as but not limited to age, gender, ethnicity, level of social support (live alone), employment.
- Relevant medical history; cardiac diagnosis, co-morbidities.

8.2.3 Baseline

Participants will have received the baseline (T1) questionnaires in the study information pack. This will include instructions to complete them within 7 days of consenting to participate and return in the stamped-addressed envelope or via e-mail to the Research Fellow. The baseline (T1) questionnaires are the 10-item Decisional Conflict Scale²³ and the bespoke coronary angioplasty knowledge questionnaire. The Research Fellow will collate returned questionnaires to determine the following outcomes:

- Number of returned self-report questionnaires at baseline (T1).
- Item response rate (Number of valid responses on each questionnaire divided by total number of responses requested).
- Number of patients who had complete data for each questionnaire at baseline.

Participant answers and questionnaire scores will be input into a CRF by the Research Fellow.

8.2.4 Pre-assessment clinic

Participants at all eight clusters will attend their usual-care pre-assessment clinic consultation with a cardiac nurse specialist which may be in-person or conducted remotely (telephone or online video call). Patient participants in the intervention arm will have received a 'communication' from the hospital confirming their pre-assessment consultation date. This may be a paper or digital letter, email, or text. Instructions on how to access CONNECT, via a web link, or QR code, will be included in the 'communication' and tailored to match the style of the Cardiology Department approach. Participants will be invited to use CONNECT and save their personal summary before attending their usual-care pre-assessment clinic consultation.

Those in the intervention group will be asked if they were able to access CONNECT and the personal summary. If available, the personal summary will be referred to during the consultation. Approaches to integrating the CONNECT summary into consultation will be discussed during the study set up training sessions. If the patient participant fails to attend the clinic consultation, their consultation will be rearranged as per usual care. Immediately following each consultation with a participant, the cardiac nurse specialist will complete the Pre-Assessment Log for collection of the following outcomes:

- Number of missed pre-assessment clinic consultations.
- Number of participants who used the CONNECT summary during the consultation
- Duration of pre-assessment clinic consultation

8.2.5 Post pre-assessment clinic (T2) questionnaires

The Clinical Research Nurse, or delegate, will liaise with the pre-assessment lead nurse weekly to update them about which patient participants had consented to study participation and attended the pre-assessment consultation. Participants at all eight clusters who attended the pre-assessment consultation will be sent four T2/Follow-up questionnaires: the Decisional Conflict Scale²³, the Coronary Angioplasty Knowledge questionnaires sent at T1/Baseline and the 10-item Preparation for Decision-Making Scale²⁴ and 13-item Perceived Involvement in Care Scale²⁵. The latter two questionnaires are validated tools designed to evaluate the quality of the decision-making process²⁶. Two extra questions will be included at the end of the Angioplasty Knowledge questionnaire to evaluate what health information patients accessed ahead of planned coronary angioplasty and their satisfaction with discussions about treatment options. In the intervention arm, two extra questions will ask whether participants were able to access CONNECT and take the personal summary to the pre-assessment appointment. Participants will be instructed to complete and return them to the Research Fellow within 7 days of receipt using the stamped-addressed envelope.

The Research Fellow will collate returned questionnaires to determine the following outcomes:

- Number of returned self-report questionnaires at post-pre-assessment.
- Number of patients who had complete data for each questionnaire at post-preassessment.
- Item response rate (Number of valid responses divided by total number of responses requested).
- Retention: defined as the proportion of participants completing the anticipated primary outcome questionnaires (i.e., completing the Decisional Conflict Scale questionnaire at T2/after pre-assessment).
- CONNECT adherence: The percentage of patient participants in the intervention arm who report being able to successfully access CONNECT and take the personal summary to the pre-assessment consultation

Participant answers and questionnaire scores will be input into a CRF by the Research Fellow.

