8.2.7 Medical record review

At the end of the study the clinical research nurse will review participants' medical records to extract and document their actual treatment/procedure received (i.e., medicines only, or coronary angiogram only, coronary angioplasty, or other (e.g. no intervention)) and medical record review for all-cause mortality, Major Adverse Cardiovascular Events (MACE), defined as acute myocardial infarction, death due to a cardiac or unknown cause, emergency revascularization, ventricular arrhythmia, or cardiogenic shock) and rates of hospital readmission, 30-days after hospital discharge.

i. Patient Questionnaires

Table 4 below shows the timepoints for the administration of measures.

Measures	Enrolment	Baseline (T1)	Post Pre- Assessment (T2)
Brief Health Literacy Screening Tool (Chew et al 2004) ²¹	Х		
eHealth Literacy Scale (Norman & Skinner 2006) ²²	Х		
Decisional Conflict Scale (O'Connor, A. 2010) ²³		X	X

Coronary Angioplasty Knowledge questionnaire. (Researcher Team generated)	Х	Х
Preparation for Decision-Making Scale (Bennett et al. 2010) ²⁴		Х
Perceived Involvement in Care Scale (Lerman et al. 1990) ²⁵		Х

Enrolment: After informed consent for study participation.

Baseline: Before using CONNECT at least 1 week before Pre-Assessment Clinic.

Post Pre-Assessment Clinic: After pre-assessment, but before coronary angio/angioplasty procedure.

The Brief Health Literacy Screening Tool is a 3-item measure designed to evaluate functional health literacy with responses recorded on a 5-point Likert scale²¹. The tool takes approximately one minute to complete, can be administered orally, performs well compared to other longer standard measures, and has been shown to have adequate validity and reliability when administered by nurses in clinic settings²⁷.

The eHealth Literacy Scale is an 8-item measure designed to evaluate peoples' knowledge, comfort, and perceived skills at accessing and using health related electronic health information with responses recorded on a 5-point Likert scale²². It is the most frequently used measure to evaluate e-literacy, has acceptable psychometric properties, but has a relatively narrow scope having been designed before the era of social media²⁸. Regardless, other comparable measures have 18-items, or more, making them impractical for use in NHS settings.

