14.3 Balancing the benefits and harms of the study

The intervention: Patient decision aid (PtDA)

There are no obvious harms from using a PtDA. A Cochrane systematic review and metaanalysis evaluating 50 different PtDAs from 105 studies, provides evidence that PtDAs are more likely to benefit patients, compared to usual care¹³. Patients receiving a PtDA are more likely to have accurate risk perception and select a treatment that is more congruent with their values and preferences. The review found no negative effect on health outcomes between the PtDA and usual care groups, indeed, some studies found a reduction in symptoms of anxiety.

In non-emergency situations, it is an ethical and legal requirement that patients provide informed consent before medical treatment. Patients must therefore be fully informed about their options. The PtDA provides comprehensive information about their treatment options (coronary angioplasty or medical therapy) including the potential risks, benefits, and side-effects. It is possible that patients may change their mind about having elective coronary angioplasty after receiving the PtDA. However, this is no different to usual care; patients in the control group who receive usual care (i.e., patient information leaflet) are also free to change their mind about having the procedure. We will record the number of patients in both groups who choose to receive medical therapy only, following referral for elective angioplasty. Receiving the PtDA will not replace consultations with the cardiologist or cardiac specialist nurse.

Participating in the interview

In the unlikely event that a participant becomes distressed during the research interview, the interview will be stopped. The participant will be given the option to terminate the interview or reconvene when they feel ready. The British Heart Foundation has a free patient line, which provides support and counselling. Details of this resource will be made available to participants and included in the participant information sheet. Participants will be able to stop the interview or withdraw from the study at any time without giving a reason. The Research Fellow will be conducting interviews alone remotely via telephone or Microsoft Teams. They can choose to end the interview if the participant displays inappropriate behaviour or makes inappropriate and personal remarks. Regular debriefs between Research Fellow and supervisory team will be scheduled.

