#### 3.3. Analysis populations

The Intention To Treat (ITT) population includes all patients for whom consent is obtained and who are randomised to treatment. This is the primary analysis set and endpoints will be summarised for the ITT population unless stated otherwise.

The Per Protocol (PP) population includes all patients who accessed CONNECT on the treatment arm. This is a secondary analysis set.

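### T2 questionnaires are triggered only by attending pre-assessment, so participants in either arm who cancel for good before that visit have no route to the anticipated primary outcome

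*Protocol*

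**What the plan says.** **Who gets T2.** Protocol 8.2.5: "Participants at all eight clusters who attended the pre-assessment consultation will be sent four T2/Follow-up questionnaires". Table 4 of the protocol times T2 as "After pre-assessment, but before coronary angio/angioplasty procedure", and SAP 2.7.4 repeats this. Neither document gives another trigger.

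**When CONNECT is used.** Protocol 8.2.4: "Participants will be invited to use CONNECT and save their personal summary before attending their usual-care pre-assessment clinic consultation".

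**Non-attendance.** Protocol 8.2.4: "If the patient participant fails to attend the clinic consultation, their consultation will be rearranged as per usual care". Missed visits are counted in the Pre-Assessment Log. Nothing is said about T2 when a visit is never rebooked.

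**Changing one's mind.** Protocol 14.3: "It is possible that patients may change their mind about having elective coronary angioplasty after receiving the PtDA". It adds that control patients "are also free to change their mind about having the procedure", and that choices of medical therapy only will be counted in both groups. Protocol 3.8 notes that decision aids have sometimes lowered uptake of discretionary surgery.

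**Analysis.** Protocol 8.2.5: "Retention: defined as the proportion of participants completing the anticipated primary outcome questionnaires", meaning the DCS at T2. SAP 3.3: "The Intention To Treat (ITT) population includes all patients for whom consent is obtained and who are randomised to treatment". SAP 4.2 plans no missing-data method, and SAP 4.1.1 plans no sensitivity analyses. The retention criterion there is Green at 80% or more of the patient sample.

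**The concern.** Attendance at pre-assessment is a post-randomisation event that follows exposure to the tool. A participant who uses CONNECT at home, settles on medicines and cancels for good has not withdrawn from the study and stays in the ITT set, yet is never asked for the outcome. Rearranging missed visits does not reach someone who does not want another one. The same happens to a control patient who cancels.

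Two results are exposed. Measured retention would mix people who were sent a questionnaire and did not return it with people who were never sent one, although these call for different remedies. The DCS difference, which SAP 4.1 uses to judge whether the effect is in a clinically relevant range and to size the full trial, would leave out people whose decision was settled early. If the rule passes unchanged into the definitive trial, so does the loss.

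**Working it through.** **1. Inputs from the documents.** Eight clusters of 40 give 320. The intervention arm is 6 × 40 = 240 (Protocol 4.3 also gives 240) and the control arm 2 × 40 = 80. The plan's own recruitment figure reproduces: 320 / 0.70 = 457.1, stated as 457. The retention Green line is 80% of the whole sample (SAP 4.1.1). The future trial assumes an effect of 0.3 to 0.4 SD and an ICC of 0.05 (SAP 2.3.2). There is no figure for opt-out before pre-assessment.

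**2. Assumptions.**
- b = 85%: T2 completion among everyone who does not opt out early.
- q = 5%, 10%, 20%: share opting out before pre-assessment.
- d = 0.5 SD: difference in mean DCS between early opt-outs and the rest.
- All consented participants are in the retention denominator. Protocol 8.2.5 says only that it is a proportion of participants.

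**3. Retention, early opt-out in the intervention arm only.** Retention = [240 × b × (1 − q) + 80 × b] / 320.

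| q | Participants never sent T2 | Intervention arm | Whole sample |
|---|---|---|---|
| 5% | 12 | 80.8% | (193.8 + 68) / 320 = 81.8% |
| 10% | 24 | 76.5% | (183.6 + 68) / 320 = 78.6% |
| 20% | 48 | 68.0% | (163.2 + 68) / 320 = 72.3% |

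The whole sample reaches 80% when 240 × 0.85 × (1 − q) = 256 − 68 = 188, so q = 1 − 188/204 = 7.8%. With b = 90% the corresponding q is 14.8%.

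**4. Retention, the same opt-out in both arms.** Retention = b × (1 − q), which is 80.8%, 76.5% and 68.0%. The Green line is crossed at q = 1 − 0.80/0.85 = 5.9%. The retention problem therefore does not depend on the arms differing.

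**5. DCS mean.** The mean over the whole arm equals the mean among those observed plus q × d, so the shift is q × d:
- 0.05 × 0.5 = 0.025 SD
- 0.10 × 0.5 = 0.05 SD
- 0.20 × 0.5 = 0.10 SD

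The largest is 25% to 33% of the 0.3 to 0.4 SD target. Its sign depends on whether early opt-outs have more or less decisional conflict than the rest, which the documents do not tell us.

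**6. Against this study's precision.** For an unadjusted comparison of 6 and 2 clusters of 40 with ICC 0.05, SE = √[(0.05 + 0.95/40) × (1/6 + 1/2)] = √(0.07375 × 0.6667) = 0.22 SD. The 95% half-width is about 0.54 SD (t, 6 df). The largest shift above is 0.10 / 0.54, under a fifth of it. The covariate adjustment in SAP 4.1 may narrow the interval somewhat.

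**The case against.** **Pre-assessment is where changes of mind belong.** The CONNECT summary, including the patient's preference, is meant to be discussed at that visit, which may be by telephone or video, and Protocol 14.3 says the decision aid does not replace consultations. A reader might infer that every intervention patient who decides against the procedure after CONNECT is lost. The documents do not support that: only those who cancel before attending are missed, and nothing says that declining the procedure means skipping the visit.

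**The rule is the same in both arms.** A reader might infer selective loss in the intervention arm. It is plausible, because the protocol anticipates that the tool may change decisions, but it is not documented, and control patients can cancel too.

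**Effects on the criteria are easy to overstate.** Subtracting ten points from 85% and comparing 75% with the Green line goes wrong twice: 10% of 85% is 8.5 points, and the line applies to the whole sample, giving 78.6%. Acceptability need not fall either. The SAP criterion is average item completion of the T2 DCS, and someone never sent the form has no responses requested. Only the protocol's preliminary criterion, the share of the sample completing the DCS, would drop. Nor is SAP 3.3 contradicted, since it defines who is in the set, not who has an outcome.

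**Some of this would be visible.** Missed visits, withdrawals with reasons, treatment received and complete-data counts by group are all recorded. They would show that data are absent without supplying the DCS.

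**A DCS taken without the consultation measures a different point.** This stands as a caution. Labelling such forms and summarising with and without them deals with it.

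What remains after all this is a stated rule that leaves permanent cancellers with no route to the outcome.

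**Conclusion.** The point holds in a limited form. Consented, non-withdrawn participants in either arm who permanently cancel before pre-assessment cannot provide the anticipated primary outcome, fail the retention definition when all consented participants are counted, and are covered by no planned missing-data method.

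The consequence that matters is for retention. With 85% completion among the others, early opt-out by about 7.8% of the intervention arm, or 5.9% of both arms, is enough to move the study from Green to Amber for a reason unrelated to willingness to complete questionnaires. The effect on the DCS mean is at most 0.10 SD over the range examined, of unknown direction, and minor beside this study's own uncertainty; it would weigh more in a definitive trial that kept the rule. All of these sizes rest on the assumed b, q and d. Unequal loss between arms is a risk to measure, not an established fact. This is an inexpensive improvement worth making, not a flaw that invalidates the study.

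**What to change.** Amend Protocol 8.2.5, and the T2 definition in Table 4 and SAP 2.7.4, as follows:

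- Send at least the DCS and the knowledge questionnaire to every consented, non-withdrawn participant. The trigger is the date attended or, if the visit is permanently cancelled, the originally scheduled date. Specify a fallback interval for anyone who cancels before a date was set.
- Record which trigger applied and the reason for non-attendance.
- State that all consented participants form the retention denominator, and report retention by arm with pre-clinic opt-outs shown separately.
- In the SAP, summarise the DCS with and without the forms completed without a visit.

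The T2 knowledge questionnaire carries the extra questions on CONNECT access, so intervention participants who never attend would also be able to report whether they reached the tool.

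The cost is slight extra postage and research-nurse time. Some T2 forms will be completed without the consultation, and the Perceived Involvement in Care Scale may not apply to non-attenders, so it can be omitted for them.
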